#### Tables with similar format:

**Table 16: Summary Statistics for SLV213 Concentrations in Plasma by Sex, 400 mg SLV213 PK Population – Day 1, Morning Dose (Single Dose)**

[**Implementation Note:** Row headers will be included labeled as “Male” and “Female”.]

**Table 17: Summary Statistics for SLV213 Concentrations in Plasma by Time Point and Dose, 400 mg SLV213 PK Population – Day 1, Evening Dose to Day 7, Morning Dose**

[Implementation Note: SLV213 plasma concentrations will be summarized for each study day from Day 1 (evening dose) to Day 7 (morning dose) for 400 mg SLV213 treatment group, and each dosing period (morning and evening). Nominal time points are  $t=0$  and 12 hours post morning dose and evening dose. The 12-hour time point is the same as the pre-dose time point of the previously received dose. Thus only  $t=12$  hours will be shown for each dose except for Day 1 (evening dose), which will also show  $t=0$  hours.]

Time Point	Dose a	Statistic	400 mg SLV213 (N=X)
Day 1	Evening (0 h)	n	x
		Mean (SD)	xx.x (xx.x)
		Geometric Mean	xx.x
		CV%	xx.x
		Median	xx.x
		Minimum, Maximum	xx, xx
	Evening (12 h)	n	
	...	...	
	Morning (12 h)	n	x
		Mean (SD)	xx.x (xx.x)
		CV%	xx.x
		Median	xx.x
		Minimum, Maximum	xx, xx
	Evening (12 h)	n	x
		...	
	Morning (12 h)	n	
	...	...	
	Day 7	n	
	Morning (12 h)	n	
		...	

Note: Concentrations are reported in units of ng/mL. Time points where data was not collected are denoted by “-”. Time points where data was not estimable are denoted by “NE”.

BQL values were imputed as 0 if they did not come after a PK sample concentration that is above the LLOQ. The first BQL value after the last PK sample concentration that is above the LLOQ is imputed as  $\frac{1}{2}$  LLOQ. All other BQL values are treated as missing.

n = Number of data points used to compute summary statistics.

SD = Standard Deviation; CV = Coefficient of Variance.

a Times are relative to time of dosing. Time 0 concentrations are drawn within 30 minutes prior to dosing. The 12-hour time point is the same as the pre-dose time point of the next received dose.

**Tables with similar format:**

**Table 18: Summary Statistics for SLV213 Concentrations in Plasma by Sex, Time Point, and Dose,  
400 mg SLV213 PK Population – Day 1, Evening Dose to Day 7, Morning Dose**

[**Implementation Note:** Row headers will be included labeled as “Male” and “Female”.]

**Table 19: Summary Statistics for SLV213 Concentrations in Plasma, 400 mg SLV213 PK Population – Day 7, Evening Dose to Day 9 (Multiple Doses)**

[Implementation Note: SLV213 plasma concentrations will be summarized for Study Day 7 (evening dose) for 400 mg SLV213 treatment group. Nominal time points are t=0, 0.5, 1, 2, 4, 6, 8, 12, 24, 36, and 48 hours post evening dose.]

Statistic	Nominal Time a (h)									
	0	0.5	1	2	4	6	12	24	36	48
n	x	x	x	x	x	x	x	x	x	x
Mean (SD)	xx.x (xx.x)	xx.x (xx.x)	xx.x (xx.x)	xx.x (xx.x)	xx.x (xx.x)	xx.x (xx.x)	xx.x (xx.x)	xx.x (xx.x)	xx.x (xx.x)	xx.x (xx.x)
SD	xx.x	xx.x	xx.x	xx.x	xx.x	xx.x	xx.x	xx.x	xx.x	xx.x
CV%	xx.x	xx.x	xx.x	xx.x	xx.x	xx.x	xx.x	xx.x	xx.x	xx.x
Median	xx.x	xx.x	xx.x	xx.x	xx.x	xx.x	xx.x	xx.x	xx.x	xx.x
Minimum, Maximum	xx, xx	xx, xx	xx, xx	xx, xx	xx, xx	xx, xx	xx, xx	xx, xx	xx, xx	xx, xx
n										
...										
n										
...										

Note: Concentrations are reported in units of ng/mL. Time points where data was not collected are denoted by “-”. Time points where data was not estimable are denoted by “NE”. BQL values were imputed as 0 if they did not come after a PK sample concentration that is above the LLOQ.

The first BQL value after the last PK sample concentration that is above the LLOQ is imputed as ½ LLOQ. All other BQL values are treated as missing.

n = Number of data points used to compute summary statistics.

SD = Standard Deviation; CV = Coefficient of Variance.

a Times are relative to time of dosing. Time 0 concentrations are drawn within 30 minutes prior to dosing.

### Tables with similar format:

**Table 20: Summary Statistics for SLV213 Concentrations in Plasma by Sex, 400 mg SLV213 PK Population – Day 7, Evening Dose to Day 9 (Multiple Doses)**

[Implementation Note: Row headers will be included labeled as “Male” and “Female”.]

**Table 21: Summary Statistics for SLV213 PK Parameters by Dose, 400 mg SLV213 PK Population**

[Implementation Note: PK parameters will only be summarized for participants with a measurable Ke at the specified dosing day.]

PK Parameter (Units)	N	Mean (SD)	GM (CV%)	Median	Minimum, Maximum
Day 1, Single Dose					
C max (ng/mL)	x	xx.x (xx.x)	xx.x (xx.x)	xx.x	xx, xx
C max /Dose (ng/mL/mg)	x	xx.x (xx.x)	xx.x (xx.x)	xx.x	xx, xx
C min (ng/mL)	x	xx.x (xx.x)	xx.x (xx.x)	xx.x	xx, xx
T max (h)	x	xx.x (xx.x)	xx.x (xx.x)	xx.x	xx, xx
AUC (0-t) (ng*h/mL)	x	xx.x (xx.x)	xx.x (xx.x)	xx.x	xx, xx
AUC (0-∞) (ng*h/mL)	x	xx.x (xx.x)	xx.x (xx.x)	xx.x	xx, xx
AUC (0-12) (ng*h/mL)	x	xx.x (xx.x)	xx.x (xx.x)	xx.x	xx, xx
AUC (0-last) (ng*h/mL)	x	xx.x (xx.x)	xx.x (xx.x)	xx.x	xx, xx
AUC (0-tau) (ng*h/mL)	x	xx.x (xx.x)	xx.x (xx.x)	xx.x	xx, xx
AUC (0-tau)/Dose (ng*h/mL/mg)	x	xx.x (xx.x)	xx.x (xx.x)	xx.x	xx, xx
t 1/2 (h)	x	xx.x (xx.x)	xx.x (xx.x)	xx.x	xx, xx
CL T (L/h)	x	xx.x (xx.x)	xx.x (xx.x)	xx.x	xx, xx
Ke (1/h)	x	xx.x (xx.x)	xx.x (xx.x)	xx.x	xx, xx
Vd (L)	x	xx.x (xx.x)	xx.x (xx.x)	xx.x	xx, xx
Day 7, Multiple Doses					
C max,ss (ng/mL)	x	xx.x (xx.x)	xx.x (xx.x)	xx.x	xx, xx
C max /Dose (ng/mL/mg)	x	xx.x (xx.x)	xx.x (xx.x)	xx.x	xx, xx
C min,ss (ng/mL)	x	xx.x (xx.x)	xx.x (xx.x)	xx.x	xx, xx
C avg (ng/mL)	x	xx.x (xx.x)	xx.x (xx.x)	xx.x	xx, xx
RC max a	x	xx.x (xx.x)	xx.x (xx.x)	xx.x	xx, xx
T max,ss (h)	x	xx.x (xx.x)	xx.x (xx.x)	xx.x	xx, xx
T min (h)	x	xx.x (xx.x)	xx.x (xx.x)	xx.x	xx, xx
AUC (0-48),ss (ng*h/mL)	x	xx.x (xx.x)	xx.x (xx.x)	xx.x	xx, xx
AUC (0-tau),ss (ng*h/mL)	x	xx.x (xx.x)	xx.x (xx.x)	xx.x	xx, xx
AUC (0-tau)/Dose (ng*h/mL/mg)	x	xx.x (xx.x)	xx.x (xx.x)	xx.x	xx, xx
Linearity Index b	x	xx.x (xx.x)	xx.x (xx.x)	xx.x	xx, xx

PK Parameter (Units)	N	Mean (SD)	GM (CV%)	Median	Minimum, Maximum
RAUC c	x	xx.x (xx.x)	xx.x (xx.x)	xx.x	xx, xx
t 1/2 (h)	x	xx.x (xx.x)	xx.x (xx.x)	xx.x	xx, xx
CL T (L/h)	x	xx.x (xx.x)	xx.x (xx.x)	xx.x	xx, xx
Vd,ss (L)	x	xx.x (xx.x)	xx.x (xx.x)	xx.x	xx, xx

Note: Single-dose parameters are calculated over the 12-hour period following the morning dose (Dose 1) on Day 1. Multiple-dose parameters are calculated over the 48-hour period following the evening dose (Dose 14) on Day 7.

N = Number of participants with an estimable Ke for the given dose used to calculate summary statistics.

SD = Standard Deviation; GM = Geometric Mean; CV = Coefficient of Variance.

a RCmax is defined as the accumulation ratio for Cmax estimated as Cmax (Day 7, Evening Dose)/Cmax (Day 1, Morning Dose).

b Linearity index is estimated as AUC(0-tau),ss (Day 7, Evening Dose)/AUC(0-x) (Day 1, Morning Dose)

c RAUC is defined as the accumulation ratio for AUC estimated as AUC(0-tau) (Day 7)/AUC(0-tau) (Day 1).

## 14.4 Safety Data

### 14.4.1 Displays of Adverse Events

**Table 22: Overall Summary of Adverse Events, Safety Population**

[**Implementation Note:** An “adverse event” includes laboratory AEs, ECG AEs, TEAEs, and other unsolicited AEs.]

Participants a with	400 mg SLV213 (N=X)		Placebo (N=X)		All Participants (N=X)	
	n	%	n	%	n	%
At least one adverse event	x	xx	x	xx	x	xx
At least one related adverse event	x	xx	x	xx	x	xx
Mild (Grade 1)	x	xx	x	xx	x	xx
Moderate (Grade 2)	x	xx	x	xx	x	xx
Severe (Grade 3)	x	xx	x	xx	x	xx
At least one severe (Grade 3) adverse event	x	xx	x	xx	x	xx
Related	x	xx	x	xx	x	xx
Unrelated	x	xx	x	xx	x	xx
At least one serious adverse event b	x	xx	x	xx	x	xx
At least one related, serious adverse event	x	xx	x	xx	x	xx
At least one adverse event leading to early termination c	x	xx	x	xx	x	xx
At least one adverse event of special interest						
At least one medically attended adverse event	x	xx	x	xx	x	xx
At least one unanticipated problem						

Note: N = Number of participants in the Safety Population.

a Participants are counted once for each category regardless of the number of events.

b Refer to Listing of Serious Adverse Events.

c As reported on the Adverse Event eCRF.

**Table 23: Serious Adverse Events and Adverse Events by MedDRA System Organ Class and Preferred Term, and Treatment Group, Safety Population**

[**Implementation Note:** If there is only one PT within a given SOC, then “Any PT” row will be omitted. An “adverse event” includes laboratory AEs, ECG AEs, TEAEs, and other unsolicited AEs. Serious adverse events will be displayed regardless of percentage of participants.]

MedDRA System Organ Class	MedDRA Preferred Term	400 mg SLV213 (N=X)			Placebo (N=X)			All Participants (N=X)		
		n	%	Events	n	%	Events	n	%	Events
Serious Adverse Events										
Any SOC	Any PT	x	xx	x	x	xx	x	x	xx	x
[SOC 1]	Any SOC	x	xx	x	x	xx	x	x	xx	x
	[PT 1]	x	xx	x	x	xx	x	x	xx	x
	[PT 2]	x	xx	x	x	xx	x	x	xx	x
	...									
[SOC 2]	Any SOC	x	xx	x	x	xx	x	x	xx	x
	[PT 1]	x	xx	x	x	xx	x	x	xx	x
...	...	x	xx	x	x	xx	x	x	xx	x
[Repeat for Other (non-serious) Adverse Events]										
Note: N = Number of participants in the Safety Population (number of participants at risk). n = Number of participants reporting event. Events = Total frequency of events reported.										

### 14.3.1.2 Treatment-Emergent Adverse Events

**Table 24: Summary of Treatment Emergent Adverse Events by MedDRA System Organ Class, High Level Group Term, Preferred Term, and Treatment Group, Safety Population**

[Implementation Note: If there is only one PT within a given SOC and HLGT, then “Any PT” row will be omitted. Similarly, if there is only one HLTG within a given SOC, then “Any HLTG” row will be omitted.]

Treatment Group	MedDRA System Organ Class	MedDRA High Level Group Term	MedDRA Preferred Term	n (%)	95% CI a	Number of Events
400 mg SLV213 (N=X)	Any SOC	Any HLTG	Any PT	x (xx)	xx, xx	x
	[SOC 1]	Any HLTG	Any PT	x (xx)	xx, xx	x
		[HLGT 1]	Any PT	x (xx)	xx, xx	x
			[PT 1]	x (xx)	xx, xx	x
	[SOC 2]	Any HLTG	Any PT	x (xx)	xx, xx	x
		[HLGT 1]	Any PT	x (xx)	xx, xx	x
			[PT 1]	x (xx)	xx, xx	x
Placebo (N=X)	...	...	...	x (xx)	xx, xx	x
	...	...	...	x (xx)	xx, xx	x
All Participants (N=X)	...	...	...	x (xx)	xx, xx	x
	...	...	...	x (xx)	xx, xx	x

Note: N = Number of participants in the Safety Population in the specified treatment group.

n = Number of participants reporting adverse events within each SOC/HLGT/PT.

A participant is only counted once per PT.

aExact Clopper-Pearson Confidence Interval.

**Table 25: Treatment Emergent Adverse Events by MedDRA System Organ Class, High Level Group Term, Preferred Term, Maximum Severity, Relationship, and Treatment Group, Safety Population**

**[Implementation Note:** If there is only one PT within a given SOC and HLGT, then “Any PT” row will be omitted. Similarly, if there is only one HLGT within a given SOC, then “Any HLGT” row will be omitted. Life-threatening severity will only be included as applicable. The highest severity for each relationship status will be reported, e.g., a participant may be counted for Mild Related and Severe Not Related for the same PT.]

Treatment Group	MedDRA System Organ Class	MedDRA High Level Group Term	MedDRA Preferred Term	Severity	Relationship to Study Treatment	
					Related n (%)	Not Related n (%)
400 mg SLV213 (N=X)	Any SOC	Any HLGT	Any PT	Any Severity	x (xx)	x (xx)
				Mild	x (xx)	x (xx)
				Moderate	x (xx)	x (xx)
				Severe	x (xx)	x (xx)
				Life-Threatening	x (xx)	x (xx)
	[SOC 1]	Any HLGT	Any PT	Any Severity	x (xx)	x (xx)
				...	x (xx)	x (xx)
		[HLGT 1]	Any PT	Any Severity	x (xx)	x (xx)
				...	x (xx)	x (xx)
			[PT 1]	Any Severity	x (xx)	x (xx)
				...	x (xx)	x (xx)
Placebo (N=X)	...	...	...		x (xx)	x (xx)
	...	...	...		x (xx)	x (xx)
All Participants (N=X)	...	...	...		x (xx)	x (xx)
	...	...	...		x (xx)	x (xx)

Note: N = Number of participants in the Safety Population in the specified treatment group.

n = Number of participants reporting adverse events within each SOC/HLGT/PT with the specified maximum severity.

A participant is only counted once per PT. A participant highest reported severity for each relationship to study treatment is reported.

### 14.3.2 Listing of Deaths, Other Serious and Significant Adverse Events

**Table 26: Listing of Serious Adverse Events**

[**Implementation Note:** If the event is ongoing (i.e., no stop date), indicate “ongoing” for “Duration”. If there are no comments, then indicate “None” for “Comments”. Listing should be sorted by Treatment Group, Participant ID, and AE Number.]

Adverse Event	Associated with Dose No.	No. of Days Post Associated Dose (Duration)	No. of Days Post Dose the Event Became Serious	Reason Reported as an SAE	Severity	Relationship to Study Treatment	If Not Related, Alternative Etiology	Action Taken with Study Treatment	Participant Discontinued Due to AE	Outcome	MedDRA System Organ Class	MedDRA High Level Group Term	MedDRA Preferred Term
Treatment Group: , Participant ID: , AE Number:													
Comments:													
Treatment Group: , Participant ID: , AE Number:													
Comments:													

**Table 27: Listing of Non-Serious, Unsolicited, Moderate or Greater Severity Adverse Events**

[Implementation Note: If the event is ongoing (i.e., no stop date), indicate “ongoing” for “Duration”. If there are no comments, then indicate “None” for “Comments”. Listing should be sorted by Treatment Group, Participant ID, and AE Number.]

Adverse Event	Associated with Dose No.	No. of Days Post Associated Dose (Duration)	Severity	Relationship to Study Treatment	If Not Related, Alternative Etiology	Action Taken with Study Treatment	Participant Discontinued Due to AE	Outcome	MedDRA System Organ Class	MedDRA High Level Group Term	MedDRA Preferred Term
Treatment Group: , Participant ID: , AE Number:											
Comments:											
Treatment Group: , Participant ID: , AE Number:											
Comments:											

**Table 28: Listing of Adverse Events of Special Interest, Medically Attended Adverse Events, and Unanticipated Problems**

[**Implementation Note:** This table is for any AESIs, MAAEs, and UPs. If the event is ongoing (i.e., no stop date), indicate “ongoing” for “Duration of Event”. If there are no comments, then indicate “None” for “Comments”. Listing should be sorted by Treatment Group, Participant ID, and AE Number.]

Adverse Event	Associated with Dose No.	No. of Days Post Associated Dose	Duration of Event	Severity	MedDRA System Organ Class	AESI?	MAAE?	UP?	Relationship	Outcome
Treatment Group: , Participant ID: , AE Number:										
Comments:										
Treatment Group: , Participant ID: , AE Number:										
Comments:										

### **14.3.3 Narratives of Deaths, Other Serious and Significant Adverse Events**

(not included in SAP, but this is a placeholder for the CSR)

#### 14.3.4 Abnormal Laboratory Value Listings (by Participant)

**Table 29: Listing of Abnormal Laboratory Results – Chemistry**

[**Implementation Note:** This listing is for any chemistry lab result outside of normal range, including ONRs and graded events. Listing will be sorted by Treatment Group, Participant ID, Laboratory Parameter, and Planned Time Point. Refer to [Section 9.6](#) for parameter sort order.]

Treatment Group	Participant ID	Sex	Age (years)	Planned Time Point	Actual Study Day	Laboratory Parameter (Units)	Result (Severity)	Relationship to Treatment	If Not Related, Alternate Etiology	Action Taken with Study Treatment	Participant Discontinued Due to Result?

**Table 30: Listing of Abnormal Laboratory Results – Hematology**

[**Implementation Note:** This listing is for any hematology lab result outside of normal range, including ONRs and graded events. Listing will be sorted by Treatment Group, Participant ID, Laboratory Parameter, and Planned Time Point. Refer to [Section 9.6](#) for parameter sort order.]

Treatment Group	Participant ID	Sex	Age (years)	Planned Time Point	Actual Study Day	Laboratory Parameter (Units)	Result (Severity)	Relationship to Treatment	If Not Related, Alternate Etiology	Action Taken with Study Treatment	Participant Discontinued Due to Result?

**Table 31: Listing of Abnormal Laboratory Results – Coagulation**

[**Implementation Note:** This listing is for any coagulation lab result outside of normal range, including ONRs and graded events. Listing will be sorted by Treatment Group, Participant ID, Laboratory Parameter, and Planned Time Point. Refer to [Section 9.6](#) for parameter sort order.]

Treatment Group	Participant ID	Sex	Age (years)	Planned Time Point	Actual Study Day	Laboratory Parameter (Units)	Result (Severity)	Relationship to Treatment	If Not Related, Alternate Etiology	Action Taken with Study Treatment	Participant Discontinued Due to Result?

**Table 32: Listing of Abnormal Laboratory Results – Urinalysis**

[**Implementation Note:** This listing is for any urinalysis lab result outside of normal range, including ONRs and graded events. Listing will be sorted by Treatment Group, Participant ID, Laboratory Parameter, and Planned Time Point. Refer to [Section 9.6](#) for parameter sort order.]

Treatment Group	Participant ID	Sex	Age (years)	Planned Time Point	Actual Study Day	Laboratory Parameter (Units)	Result (Severity)	Relationship to Treatment	If Not Related, Alternate Etiology	Action Taken with Study Treatment	Participant Discontinued Due to Result?

### 14.3.5 Displays of Laboratory Results

#### 14.3.5.1 Chemistry Results

##### Table 33: Chemistry Laboratory Results by Parameter, Maximum Severity, Time Point, and Treatment Group, Safety Population

[Implementation Note: Chemistry results will be presented for Check-In (Day -1)(baseline), 2, 4, 6, and 8 and for each treatment group.

If there are no life-threatening/grade 4 chemistry results reported, then the rows will be omitted. If there is not at least one graded event for a treatment group within a parameter, then only “None” row will be shown. If there are more than one graded event within a parameter for a specified time point, then report the maximum severity.

If the grade is zero counts, then populate the cell with “-”.

Parameters will be shown in the following order: Any Chemistry Parameter, Sodium, Potassium, Total Carbon Dioxide, Calcium, Creatinine, Blood Urea Nitrogen, Fasting Glucose, Total Protein, Albumin, Total Bilirubin, Alanine Aminotransferase, Aspartate Aminotransferase, Alkaline Phosphatase, Amylase, Lipase, Magnesium, and Inorganic Phosphorus.

Parameters will specify increase or decrease. If a parameter can both increase and decrease, then the parameter decrease will be listed first.

The following parameters may decrease: Sodium, Potassium, Total Carbon Dioxide, Calcium, Total Protein, Albumin, Magnesium, and Inorganic Phosphorus.

The following parameters may increase: Sodium, Potassium, Total Carbon Dioxide, Calcium, Creatinine, Blood Urea Nitrogen, Fasting Glucose, Total Bilirubin, Alanine Aminotransferase, Aspartate Aminotransferase, Alkaline Phosphatase, Amylase, and Lipase.]

Severity	Treatment Group	Day -1 (Baseline)		Day 2		Day 4		Day 6		Day 8		Any Time Post Baseline	
		n/N	%	n/N	%	n/N	%	n/N	%	n/N	%	n/N	%
Any Chemistry Parameter													
None	400 mg SLV213	x/x	xx	x/x	xx	x/x	xx	x/x	xx	x/x	xx	x/x	xx
	Placebo												
	All Participants												
Mild	400 mg SLV213												
...	...												

**Table 33: Chemistry Laboratory Results by Parameter, Maximum Severity, Time Point, and Treatment Group, Safety Population (continued)**

Severity	Treatment Group	Day -1 (Baseline)		Day 2		Day 4		Day 6		Day 8		Any Time Post Baseline	
		n/N	%	n/N	%	n/N	%	n/N	%	n/N	%	n/N	%
Moderate	400 mg SLV213												
	...												
Severe	400 mg SLV213												
	...												
Life-Threatening	400 mg SLV213	X	XX	X	XX	X	XX	X	XX	X	XX	X	XX
	...												
Sodium, Decrease													
None	400 mg SLV213												
...	...												
Mild	400 mg SLV213												
	...												
Moderate	400 mg SLV213	X	XX	X	XX	X	XX	X	XX	X	XX	X	XX
	...												
Severe	400 mg SLV213												
	...												
Life-Threatening	400 mg SLV213												
	...												

**Table 33: Chemistry Laboratory Results by Parameter, Maximum Severity, Time Point, and Treatment Group, Safety Population (continued)**

Severity	Treatment Group	Day -1 (Baseline)		Day 2		Day 4		Day 6		Day 8		Any Time Post Baseline	
		n/N	%	n/N	%	n/N	%	n/N	%	n/N	%	n/N	%
Sodium, Increase													
None	400 mg SLV213												
...	...												
[Repeat for each chemistry parameter]													
Note: The “Any Time Post Baseline” column indicates the maximum severity experienced by each participant at any time point post baseline, including unscheduled assessments. Abnormal laboratory events were only considered an adverse event if the graded severity worsened from baseline.													
N = Number of participants in the Safety Population with the laboratory result assessed at the respective time point; n = Number of participants with the maximum grade experienced for the specified parameter and time point.													

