## 9.6. Clinical Laboratory Evaluations

Venipuncture schedule and blood volumes are shown in schedule of assessments ([Table 3](#)). Unscheduled clinical laboratory evaluations will be included in listings of all clinical laboratory results but will be excluded from tabular and graphical summaries by time point, except when calculating the maximum severity post baseline. All clinical laboratory results will be listed for each participant from time of screening to last study visit. Any abnormal laboratory result at Screening or Check-in (Day -1) (baseline) with values in the Grade 1 range but deemed acceptable for enrollment per [Section 4.3.1](#), inclusion criterion #4, will be presented in listings but will only be reported as a TEAE if severity worsens. Clinical laboratory parameters that have grading criteria for both decreases (result lower than normal range) and increases (result higher than normal range) will be summarized separately by direction.

Laboratory results will be presented for chemistry, hematology, coagulation, and urinalysis separately. All safety laboratory results, severity, and change from baseline will be listed for each participant by treatment group, parameter, and time point in [Listing 13](#), [Listing 14](#), [Listing 15](#), and [Listing 16](#). Abnormal laboratory results (laboratory results outside the site normal range) will be presented in [Table 29](#), [Table 30](#), [Table 31](#), and [Table 32](#). Laboratory results outside of normal range but not within toxicity grading ranges will be listed as “ONR” (out of normal range) for severity.

The sort order for CHEM parameters will be as follows: Sodium, Potassium, Total Carbon Dioxide, Calcium, Chloride, Creatinine, eGFR, Blood Urea Nitrogen, Fasting Glucose, Total Protein, Albumin, Total Bilirubin, Direct Bilirubin, Alanine Aminotransferase, Aspartate Aminotransferase, Alkaline Phosphatase, Amylase, Lipase, Magnesium, and Inorganic Phosphorus.

The sort order for HEM parameters will be as follows: Hemoglobin, Platelets, Red Blood Cells, White Blood Cells, Neutrophils, Lymphocytes, Monocytes, Basophils, and Eosinophils.

The sort order for COAG parameters will be as follows: PT INR, Prothrombin Time, and aPTT.

The sort order for UA parameters will be as follows: pH, Specific Gravity, Bilirubin, Nitrite, Urine Protein, Urine Glucose, Occult Blood, White Blood Cell Count, Red Blood Cell Count, and Bacteria.

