Potassium increase – mmol/L	5.1 – 5.2	5.3 – 5.4	5.5 – 5.6	> 5.6
Potassium increase – mmol/L	3.5 – 3.6	3.3 – 3.4	3.1 – 3.2	< 3.1
Carbon Dioxide increase – mEq/L	32.1 – 36.0	36.1 – 40.0	> 40.0	Intervention indicated
Carbon Dioxide decrease – mEq/L	17.0 – 21.9	14.0 – 16.9	< 14.0	Metabolic acidosis Invention indicated
Calcium increase – mg/dL	10.5 – 11.0	11.1 – 11.5	11.6 – 12.0	> 12.0
Calcium decrease – mg/dL	8.0 – 8.4	7.5 – 7.9	7.0 – 7.4	< 7.0
Creatinine increase – mg/dL	1.50 – 1.79	1.80 – 2.00	2.01 – 2.50	> 2.50
BUN increase – mg/dL	23 – 26	27 – 31	> 31	Requires dialysis
Glucose (fasting) increase – mg/dL	100 - 110	111 - 125	>125	Insulin requirements or hyperosmolar coma
Glucose (fasting) decrease – mg/dL	65 – 69	55 – 64	45 – 54	< 45
Total Protein decrease – g/dL	5.5 – 6.0	5.0 – 5.4	< 5.0	--
Albumin decrease – g/dL	2.8 – 3.1	2.5 – 2.7	< 2.5	--
Total Bilirubin increase – mg/dL, when LFT  normal	1.5 – 2.1	2.2 – 2.7	2.8 – 4.2	> 4.2
Total Bilirubin increase – mg/dL, when LFT  increased	1.5 – 1.6	1.7 – 2.1	2.2 – 2.4	> 2.4
Alanine Aminotransferase (SPGT/ALT) increase – U/L, female male	44 – 100 60 – 137	101 – 200 138 – 275	201 – 400 276 – 550	> 400 > 500
Aspartate Aminotransferase (SGOT/AST) increase – U/L, female male	38 – 87 55 – 125	88 – 175 126 – 250	176 – 350 251 – 500	> 350 > 500
Alkaline Phosphatase (ALP) increase – U/L, female male	114 – 208 141 – 258	209 – 312 259 – 387	313 – 1040 388 – 1290	> 1040 > 1290
Amylase increase – U/L	110 – 150	151 – 200	201 – 500	> 500
Lipase increase – U/L	66 – 90	91 – 201	121 – 300	> 300
Magnesium decrease – mg/dL	1.30 – 1.50	1.10 – 1.29	0.90 – 1.09	< 0.90
Phosphorus (inorganic) decrease – mg/dL	2.3-2.5	2.0 – 2.2	1.6 – 1.9	< 1.6
Hematology				
Hemoglobin decrease – g/dL, female male	11.0 – 12.0 12.5 – 13.5	9.5 – 10.9 10.5 – 12.4	8.0 – 9.4 8.5 – 10.4	< 8.0 < 8.5
Hemoglobin decrease – g/dL,	Any decrease – 1.5	1.6 – 2.0	2.1 – 5.0	> 5.0

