#### 14.3.5.2 Hematology Results

##### Table 34: Hematology Laboratory Results by Parameter, Maximum Severity, Time Point, and Treatment Group, Safety Population

[Implementation Note: This table will be a similar format to [Table 33](#).

Parameters will be shown in the following order: Any Hematology Parameter, Hemoglobin, Platelets, White Blood Cells, Neutrophils, Lymphocytes, Monocytes, Basophils, and Eosinophils.

The following parameters may decrease: Hemoglobin, Platelets, White Blood Cells, Neutrophils, and Lymphocytes.

The following parameters may increase: Hemoglobin, White Blood Cells, Monocytes, Basophils, and Eosinophils.]

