#### 14.3.5.3 Urinalysis Results

##### Table 36: Urinalysis Laboratory Results by Parameter, Maximum Severity, Time Point, and Treatment Group, Safety Population

[Implementation Note: This table will be a similar format to [Table 33](#). Urinalysis will be presented for Days -1 (baseline), 4, and 8 and for each treatment group. Headers will not be split into Low and High, e.g., “Mild/Grade 1”.

Parameters will be shown in the following order: Any Urinalysis Parameter, Bilirubin, Nitrite, Urine Protein, Urine Glucose, White Blood Cell Count, Red Blood Cell Count, and Bacteria.

Urine microscopy parameters (WBC Count, RBC Count, and Bacteria) were only collected conditionally and thus will only be included if at least 5 participants reported a graded event. Otherwise refer to [Table 32](#).]

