### 14.3.6 Displays of Vital Signs

**Table 37: Supine Vital Signs by Assessment, Maximum Severity, Time Point, and Treatment Group, Safety Population**

**[Implementation Note:** Vital signs will be presented for Days 1 (pre-dose 1)(baseline) through Day 9 for each treatment group. Dosing days (Days 1 through 7) will be separated by pre- and post- Morning and Evening dose. Follow-up assessments and Maximum Post Baseline will be Any Time.

If there are no life-threatening/grade 4 vital signs reported, then the columns will be omitted. If there is not at least one graded event for a treatment group within a parameter, then only “Max Severity Post Baseline” will be shown. If there are more than one graded event within a parameter for a specified time point, then report the maximum severity.

For grading not applicable to the specified parameter, then populate the cell with “N/A”. Otherwise, if the grade is zero counts, then populate the cell with “-”. Assessments will be shown in the following order: Any Vital Sign Assessment, Oral Temperature, Systolic Blood Pressure, Diastolic Blood Pressure, Pulse, and Respiratory Rate.

Assessments will specify low or high. If an assessment can be both high and low, then the low assessment will be listed first.

The following assessments may be low: Systolic Blood Pressure, Diastolic Blood Pressure, and Pulse.

All assessments may be high.]

Time Point	Dose	Treatment Group	N	None		Mild/ Grade 1		Moderate/ Grade 2		Severe/ Grade 3		Life-Threatening/ Grade 4	
				n	%	n	%	n	%	n	%	n	%
Any Vital Sign Assessment													
Day 1	Pre-Morning (Baseline)	400 mg SLV213	x	x	xx	x	xx	x	xx	x	xx	x	xx
		Placebo											
		All Participants											
	Post-Morning	400 mg SLV213											
		...											
	Pre-Evening	400 mg SLV213											
		...											
	Post-Evening	400 mg SLV213											
		...											

**Table 37: Supine Vital Signs by Assessment, Maximum Severity, Time Point, and Treatment Group, Safety Population (continued)**

Time Point	Dose	Treatment Group	N	None		Mild/ Grade 1		Moderate/ Grade 2		Severe/ Grade 3		Life-Threatening/ Grade 4	
				n	%	n	%	n	%	n	%	n	%
Day 2	Pre-Morning	400 mg SLV213											
		...											
	Post-Morning	400 mg SLV213											
		...											
	Pre-Evening	400 mg SLV213											
		...											
	Post-Evening	400 mg SLV213											
		...											
...	...	...											
Day 8	N/A	400 mg SLV213											
		...											
Day 9	N/A	400 mg SLV213											

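### SAP Table 33 has no row for graded low fasting glucose, and Table 36 withholds graded urine microscopy below 5 participants, so the severity-by-arm tables fall short of what SAP 9.6 promises

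*SAP*

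**What the plan says.** SAP 9.6 sets the rule. For "Clinical laboratory parameters that have grading criteria for both decreases (result lower than normal range) and increases (result higher than normal range", each direction is to be summarised on its own. The same section promises numbers and percentages by severity, parameter, time point and treatment group for chemistry (Table 33), hematology (Table 34), coagulation (Table 35) and urinalysis (Table 36). It sets no minimum count for any of them.

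SAP Table 8 has a graded row for "Glucose (fasting) decrease – mg/dL": 65–69, 55–64, 45–54 and below 45 mg/dL for Grades 1 to 4. The same table grades a fasting glucose increase. The note to Table 33 lists the decreases as "The following parameters may decrease: Sodium, Potassium, Total Carbon Dioxide, Calcium, Total Protein, Albumin, Magnesium, and Inorganic Phosphorus"; fasting glucose appears only in the increase list.

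For urine microscopy (white cells, red cells, bacteria), the note to Table 36 says the rows "will only be included if at least 5 participants reported a graded event". Its reason is that microscopy was collected conditionally, and it otherwise sends the reader to the listing in Table 32.

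Three rows run the other way. Table 34 says "The following parameters may increase: Hemoglobin, White Blood Cells, Monocytes, Basophils, and Eosinophils", but Table 8 grades hemoglobin decreases only. Table 37 says "The following assessments may be low: Systolic Blood Pressure, Diastolic Blood Pressure, and Pulse", but Table 7 grades systolic hypotension only. Table 36 has a urine bilirubin row, which SAP 4.5.1 says is not graded.

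**The concern.** Type, incidence and severity of laboratory adverse events are part of the primary safety endpoint (SAP section 3). Tables 33 to 36 are where the plan sets laboratory severity out by arm and visit over participants tested. A programmer follows the implementation notes, so a direction absent from the note is absent from the table.

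For glucose, a value of 50 mg/dL is Grade 3 in Table 8. It would count in the Grade 3 laboratory line of Table 14, yet no glucose row of Table 33 would show it. In the fasting glucose increase block that participant would fall under no severity. The two tables would not reconcile, and nothing in the SAP would tell the reader why. Glucose is drawn fasting, before the morning dose on Days 2, 4 and 6 and again on Day 8, so low values are not far-fetched.

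For microscopy, a display threshold in a trial this small can remove a graded parameter from the by-arm comparison altogether. Dipstick occult blood is not graded (SAP 4.5.1), so no other row of Table 36 stands in for graded urinary red cells.

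**Working it through.** No power or alpha calculation applies: the trial tests no hypothesis and its size was not based on power. The check compares each graded parameter-direction in SAP Tables 7 and 8 with the rows the shell notes allow. The low-potassium row of Table 8 (3.5–3.6 down to below 3.1 mmol/L) is labelled as an increase; I read it as a decrease from its values.

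| Shell | Direction | Graded | Rows | Difference |
|---|---|---|---|---|
| Table 33 | decrease | 9 | 8 | fasting glucose graded, no row |
| Table 33 | increase | 13 | 13 | none |
| Table 34 | decrease | 5 | 5 | none |
| Table 34 | increase | 4 | 5 | hemoglobin row, no grade |
| Table 36 | not split | 6 | 7 | urine bilirubin row, no grade |
| Table 37 | low | 2 | 3 | diastolic row, no grade |
| Table 37 | high | 5 | 5 | none |

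The totals close: 9 + 13 + 5 + 4 + 6 + 2 + 5 = 44 graded directions; 44 − 1 without a row + 3 rows without a grade = 46 = 8 + 13 + 5 + 5 + 7 + 3 + 5. The nine chemistry decreases in Table 8 are sodium, potassium, carbon dioxide, calcium, glucose, total protein, albumin, magnesium and phosphorus. Table 33 lists all but glucose.

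**The threshold in Table 36.** SAP section 5 plans 12 per cohort, 8 active and 4 placebo. SAP 6.2 reports four replacements in Cohort 1, so up to 12 + 4 = 16 dosed if all planned and replacement participants were dosed.

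- Counted overall: 5/12 = 41.7%; 5/16 = 31.3%.
- Counted per arm, planned sizes: 5/8 = 62.5% of active; a placebo group of 4 could never reach 5. (SAP Table 4 gives different group sizes from section 5. Its total, 6 + 6 + 6 + 18 = 36, is also 12 per cohort if placebo is spread evenly, so the overall figure does not depend on which is right.)

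To show how demanding the overall reading is, let each participant independently have a graded microscopy result with probability p. The documents give no value, so p is an assumption shown over a range. The rows appear with probability P(X ≥ 5) = 1 − Σ C(n,k) p^k (1−p)^(n−k), k = 0 to 4:

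| p | n = 12 | n = 16 |
|---|---|---|
| 0.05 | 0.0002 | 0.0009 |
| 0.10 | 0.0043 | 0.0170 |
| 0.20 | 0.0726 | 0.2018 |
| 0.30 | 0.2763 | 0.5501 |

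**A limit on that picture.** Table 8 makes urine white cells of 0–10 per high-power field Grade 1, so every white-cell result is graded by construction. For that parameter the threshold in effect asks whether 5 participants had microscopy at all.

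**The case against.** The strongest reply is that Tables 33 to 36 are not the only by-arm output. The notes to Tables 22 and 23 say that adverse events include laboratory ones, so a low glucose that worsens from baseline and is reported as an adverse event is counted by arm in Tables 22 to 25, with an exact interval in Table 24 and maximum severity in Table 25. Table 14 counts participants with Grade 3 laboratory results without restricting the parameter. Low glucose results appear in Table 29 and Listing 13, and microscopy results in Table 32 and Listing 16. The body text of SAP 9.6 already states the right rule, so the glucose omission is a slip in one shell. The microscopy threshold is disclosed, with its reason and a pointer to Table 32.

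All of this stands, and it sets the size of the point. A reader might infer that graded low glucose or urinary red cells would vanish from the report, or that the primary safety endpoint would be undercounted. The documents do not support either reading.

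What the reply does not remove is the conflict. The adverse event tables are not by visit and do not use participants tested as the denominator. Conditional collection of microscopy is a reason to change the denominator; SAP 9.6 gives no basis for leaving the rows out.

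The rows without a grade do little harm. In the Table 33 format, which Table 34 follows, a parameter with no graded event collapses to a single row showing none. Table 37 fills inapplicable grades as not applicable and otherwise shows only the maximum-severity row. The potassium label is clerical: its values are unambiguous, and Table 33 lists potassium in both directions.

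**Conclusion.** The point holds as a reporting gap confined to the severity-by-arm tables. Fasting glucose decrease is the one graded direction of the 44 checked, and 1 of the 9 chemistry decreases, with no row. That contradicts SAP 9.6, and the shell does not say whether the row for any chemistry parameter counts it. The 5-participant rule in Table 36 also conflicts with SAP 9.6 and leaves its unit undefined; read overall it is 42% of the planned 12, or 31% of 16 if all planned and replacement participants were dosed.

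It should not be read as concealment, as loss of data, or as a change to any adverse event count, population or grading rule. Nor do the documents show that such events occurred; the binomial figures describe the rule under assumed rates only. The ungraded rows and the potassium label are tidying.

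**What to change.** 1. Table 33: add fasting glucose to the decrease list, and state that the row for any chemistry parameter counts graded results in both directions, low glucose included.
2. Table 36: remove the 5-participant threshold and show white cells, red cells and bacteria as n/N of participants tested. Footnote that testing followed an abnormal dipstick, and that Table 8 grades urine white cells of 0–10 per high-power field as Grade 1, so a graded count in that row does not by itself indicate abnormality. Without that footnote the row would read 100% graded by construction. State whether the row for any urinalysis parameter includes microscopy.
3. Tidying: mark hemoglobin increase (Table 34), low diastolic pressure (Table 37) and urine bilirubin (Table 36) as not graded, and relabel the low-potassium row of Table 8 as a decrease.

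The cost is a few lines of shell text and some programming, with no new data. SAP section 15 allows changes by addendum before final data lock and rules out amendment afterwards, so this belongs before lock.
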